### **7.3.2 Other Restrictions**

Regular use of more than 2 standard drinks of alcohol per day is prohibited. In the United States, a standard drink contains about 14 grams of alcohol. This roughly corresponds to a 12-fluid ounce (350 mL) glass of beer (5% alcohol by volume [ABV]), a 5-fluid ounce (150 mL) glass of wine (12% ABV), or a 1.5-fluid ounce (44 mL) glass of a spirit (40% ABV).

Use of any illicit drugs is prohibited throughout the study period.

## **8 EFFICACY ASSESSMENTS**

### **8.1 Electroencephalogram**

A standard multi-lead video-EEG with HV and photic stimulation (PS) will be obtained over 30 minutes and will be followed by an additional 6-hour awake video-EEG (total, 6.5 hours). HV will be conducted under the protocol used in the NIH-sponsored childhood absence study ([Glauser et al., 2010](#)). The first 30 minutes will consist of HV and PS. For HV, subjects will be hyperventilated for 5 minutes or until the subject has an absence seizure (HV period 1). If no absence seizure occurs during HV period 1, the subject will rest for 5 minutes and then perform hyperventilation for an additional 5 minutes (HV period 2). Photic stimulation will be performed as described in the EEG charter. The EEG will be centrally evaluated by a qualified rater. After completion of the above 30-minute video-EEG during which HV and PS are carried out, the video-EEG will continue, and the subjects will be monitored during wakefulness for an additional 6 hours (total, 6.5 hours). The EEG recording will be centrally evaluated by a qualified rater. Procedures for VH, PS and video-EEG will be elaborated in the EEG Charter.

### **8.2 Seizure-related Disability Assessment Scale**

The SERDAS was developed to assess functional impairment in work/school, social, and family life. The SERDAS is a 6-item self-report tool on which the patient rates the extent to which work/school, social life, and homelife or family responsibilities are impaired by his or her symptoms on a 10-point visual analog scale.

### **8.3 Daily Seizure Diary**

Beginning at the screening visit and continuing each day until the End of Study Visit, subjects will document if they had any absence seizures on that day (absence seizure-free

day). The number of absence seizure-free days will be calculated during both the baseline period and the treatment period.

## **9 PHARMACOKINETIC AND PHARMACOGENOMIC ASSESSMENTS**

### **9.1 Blood Sample Collection for Pharmacokinetic Assessments**

For details on the timing, volume, handling, storage, and methods of analysis of blood samples see the Laboratory Manual.

### **9.2 Pharmacokinetic Parameters**

Plasma concentrations of CX-8998 and its metabolites (including, but not limited to, M01 and M02) will be determined.

The concentrations of CX-8998 and its metabolites (including, but not limited to, M01 and M02) in plasma will be summarized by visit, timepoint and dose using descriptive statistics.

The concentration data will also be used as part of an exploratory population PK/PD analysis intended to evaluate the exposure-response and exposure-safety relationships, which will be reported separately from the clinical study report.

### **9.3 Pharmacogenomics of Drug Response**

Genomic and metabolomic variation may help to explain some of the variability in response seen with some drugs among different individuals. This is referred to as pharmacogenomics. Comparing the DNA, RNA, protein, and metabolite variation patterns of subjects who respond well and those who respond poorly to treatment may help to better define the most appropriate group of subjects in which to target a given treatment. Collecting and retaining samples for pharmacogenomic analyses makes it possible to seek explanations for differences in, for example, exposure, efficacy, tolerability, or safety not anticipated prior to the beginning of the study.

An optional 4-mL blood sample will be collected at Visit 1/baseline and retained for potential pharmacogenomic analyses related to drug response for subjects who consent to provide sample for these potential analyses. For example, putative safety biomarkers, drug metabolizing enzyme genes, drug transport protein genes, or genes thought to be related to the mechanism of drug action may be examined. Detailed collection, processing, storage and shipment instructions are provided in the Laboratory Manual.

## **10        SAFETY ASSESSMENTS**

### **10.1      Assessment of Safety**

#### **10.1.1    Adverse Events**

Adverse events (AEs) will be captured from the time the ICF is signed through the EOS telephone safety check on Day 33. SAEs will be reported up to 30 days after the last dose of study drug. A follow-up phone call will be made 30 days after the last dose of study drug for evaluation of any SAEs. See [Section 10.2](#) for definitions and instructions on the rating and collection of AEs.

#### **10.1.2    Physical and Neurological Examinations**

A complete physical examination includes measurement of height (screening only), weight, and examination of general appearance, skin, neck (including thyroid), eyes, ears, nose, throat, heart, lungs, abdomen, lymph nodes, and extremities. Genital, rectal, and breast examination may be excluded if not clinically indicated. Weight should be measured on the same scale each time. A neurological examination includes testing mental status, gait, cerebellar function, cranial nerves, motor functioning (including strength and reflexes), and sensation.

The targeted physical examination is at the investigator's discretion based on subject reported signs and symptoms and investigator observations.

#### **10.1.3    Vital Signs**

Vital signs include body temperature, systolic and diastolic blood pressures, pulse rate, and respiration rate.

Blood pressure and pulse rate will be measured in the recumbent position after at least 2 minutes of recumbency, and both will be measured again after approximately no less than 1 minute of standing. Subjects should be observed carefully for dizziness or unsteadiness while standing and allowed to sit if such occurs. Blood pressure and pulse rate should be recorded as soon as possible after sitting if the subject cannot stand for 1 full minute.

Recumbent and standing recordings of blood pressure and pulse rate will be made at the Screening Visit and at the Day 26 Visit. Orthostatic blood pressure and pulse rate will be measured before dosing (recumbent and standing) on Day 1. During any visit (screening, baseline, or Day 26 or an unscheduled clinic visit), blood pressure and pulse rate are to be assessed at any time subjects appear faint or complain of dizziness or other symptoms suggestive of hypotension.

Respiratory rate and temperature will be measured in the recumbent position and need only be measured one time (with the first set of blood pressure/pulse measurements)

#### **10.1.4      Clinical Laboratory Tests**

The following screening/safety laboratory tests (hematology, chemistry, and urinalysis) will be performed after 4 to 6 hours of fasting:

- Hematology testing will include hematocrit, hemoglobin, red blood cell count, white blood cell (WBC) count with differential, absolute neutrophil count (ANC), and absolute lymphocyte count (ALC), and platelet count.
- Serum chemistry analyses will include sodium, potassium, chloride, calcium, magnesium, phosphorus, bicarbonate, albumin, total protein, glucose, blood urea nitrogen (BUN), creatinine, creatine kinase (CK), uric acid, lactate dehydrogenase (LDH), ALT, AST, alkaline phosphatase, triglycerides, total cholesterol, and total bilirubin.
- Urinalysis will be performed only as clinically indicated.

#### **10.1.5      Urine Drug Screen**

Subjects will undergo urine drug screening for the presence of phencyclidine (PCP), cocaine, cannabinoids, opiates/barbiturates, benzodiazepines, amphetamines, methadone, and MDMA (Ecstasy) at the Screening Visit and at the Day 26 Visit. Subjects who have a positive urine drug screen will be excluded from the study unless the positive result is explained by the use of an approved prescription medication.

#### **10.1.6      Pregnancy Tests**

A urine pregnancy test will be performed for all WOCBP. See [Section 6.2](#), inclusion criterion #10 for the definition of WOCBP.

Positive urine tests will be confirmed with a serum pregnancy test. Subjects may not enter the study if pregnant and must be immediately be discontinued from dosing when a positive pregnancy test is reported during study participation.

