**Table 3 Schedule of Assessments**

Visit	Screening	Dosing Period										EOT	EOS	FU	
		Day	-28 to -1	1	2	3-7	8	9-13	14	15-19	20	21-25			
Visit Window			-	0		-2 d		-2 d		-2 d			±1 d	±1 d	±2 d
CX-8998 daily dose	-		4 mg		8 mg		12 mg		16 mg		20 mg				
Clinic visit	X	X										X 			
Telephone call 				X		X 		X 		X 			X 	X	
Informed consent 	X														
Demography/medical history 	X														
Eligibility criteria	X	X													
Complete physical exam	X											X			
Targeted physical exam 		X													
Neurological exam	X											X			
Vital signs 	X	X										X			
Electrocardiogram 	X	X										X			
Clinical laboratory tests 	X	X										X			
Urine (+/- serum) pregnancy test 	X											X			
Serum FSH 	X														
Drug screening 	X											X			
Pharmacogenomics sample 		X													
Blood sampling for PK 		X										X			
Video EEG + HV and PS 	X											X			
Video-EEG 	X											X			
Seizure-related Disability Assessment Scale		X										X			

Visit	Screening	Dosing Period										EOT	EOS	FU
Day	-28 to -1	1	2	3-7	8	9-13	14	15-19	20	21-25	26	33	57	
Visit Window		-	0		-2 d		-2 d		-2 d		±1 d	±1 d	±2 d	
CX-8998 daily dose	-	4 mg		8 mg		12 mg		16 mg		20 mg				
Clinic visit	X	X									X 			
Telephone call 			X		X 		X 		X 			X 	X	
Daily Seizure Diary	X	X	X	X	X	X	X	X	X	X				
C-SSRS 	X	X									X			
UM-PDHQ 		As needed												
Prior / concomitant meds	X	X			X		X		X		X			
AE review 		X			X		X		X		X	X	X 	
Study drug admin. in clinic		X 									X 			
Study drug admin. outpatient		X 	X	X	X	X	X	X	X	X	X 			
Drug compliance											X 			

AE = adverse event; C-SSRS = Columbia-Suicide Severity Rating Scale; ECG = electrocardiogram; EEG = electroencephalogram; EOS = end of study; EOT = end of treatment; FSH = follicle-stimulating hormone; FU = follow-up; HIV = human immunodeficiency virus; HV = hyperventilation, PK = pharmacokinetic;

PS = photic stimulation; UM-PDHQ – University of Miami Parkinson’s Disease Hallucinations Questionnaire.

1. Visit window ± 1 day as needed for scheduling.

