2. Visit window +0, -2 days as need for scheduling.
3. Before initiating dose escalation, study staff will contact the subjects by telephone and will question them about their health status, including about the occurrence of any AEs. Subjects who report AEs may be asked to return to the clinic for an unscheduled visit. Subjects who are suspected of experiencing a neuropsychiatric event should be seen in person.
4. Informed consent must be signed prior to initiation of all other screening procedures.
5. Medical history will include seizure history.
6. A targeted physical exam will be based on subject reports of signs and symptoms and investigator’s observations.
7. Vital signs include body temperature, systolic and diastolic blood pressures, pulse rate and respiration rate. Vital signs will be collected predose and postdose (1-2 hours) at the Baseline (Day 1) Visit and during the Day 26 clinic visit. Blood pressure and pulse rate will be measured in the recumbent position after at least 2 minutes of recumbency, and both will be measured again after approximately no less than 1 minute of standing.
8. At baseline (Day 1), a 12-lead ECG will be performed predose and approximately 1-2 hours after the dose as convenient between other required visit procedures. All ECGs should be performed after at least 10 minutes of recumbency.

9. Clinical chemistry, and hematology. Urinalysis to be performed only as clinically indicated. Additional lab tests are obtained at the screening visit to verify eligibility (including HIV, hepatitis B and C). A positive drug screen will result in exclusion from the study unless it is explained by use of an allowed prescription medication.
10. A urine pregnancy test will be performed, and if the result is positive a serum pregnancy test should be completed.
11. Serum FSH only as needed to determine menopausal status in females <62 years old with history of ≥12 months of amenorrhea without another cause.
12. Laboratory urine testing for phencyclidine (PCP), cocaine, cannabinoids, opiates, barbiturates, benzodiazepines, amphetamines, methadone, and MDMA (Ecstasy).
13. Optional sample that requires additional informed consent.

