14. On Day 1, PK samples will be taken at time 0 (predose; before subject takes first dose of study drug in the clinic) and at 1, 2, and 4 hours after administration of study drug. Two postdose PK samples, separated by >2 hours, will be obtained on Day 26. The time of the last dose of study drug and the time of the blood draw will be recorded.
15. A standard multi-lead 6.5-hour video EEG will be obtained using HV and PS. The first 30 minutes will consist of HV and PS. For HV, subjects will be hyperventilated for 5 minutes or until the subject has an absence seizure (HV period 1). If no absence seizure occurs during HV period 1, the subject will rest for 5 minutes and then perform hyperventilation for an additional 5 minutes (HV period 2). Photic stimulation will be performed as described in the EEG charter. The EEG will be centrally evaluated by a qualified rater.
16. After completion of the above 30-minute video-EEG during which HV and PS are conducted, the video-EEG will continue, and the subjects will be monitored during wakefulness for an additional 6 hours. The EEG recording will be centrally evaluated by a qualified rater.
17. The “Lifetime” version of the C-SSRS will be used at screening, and the “Since Last Visit” version will be completed at all other visits.
18. The UM-PDHQ is a 20-item clinician-administered questionnaire that quantitatively and qualitatively assesses hallucinations. The UM-PDHQ will be completed for any subject who reports hallucinations.
19. All AEs, irrespective of the relatedness to the study drug, will be captured from the time the ICF is signed through the EOS visit. All AEs should be followed until resolution, for 30 days after onset, for 30 days after the last dose of study drug, until the subject is lost to follow-up (as defined in [Section 6.4.1](#)), or the subject withdraws consent, whichever occurs first. Serious adverse events (SAEs) will be reported up to 30 days after the last dose of study drug. A follow-up phone call will be made 30 days after the last dose of study drug for evaluation of any SAEs.
20. Study drug will be administered in the clinic on the morning of Day 1. Study drug will be administered on an outpatient basis on the evening of Day 1 through the morning of Day 26. Subjects will be instructed to bring all used empty bottles and unused study drug, with them to the end-of-study visit on Day 26.
21. Drug compliance will be assessed by capsule count.

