## 7.2 Summary of Treatment Visits

### 7.2.1 Screening

The Screening Visit must be performed within 28 days of Visit 1/baseline. Subject informed consent must be obtained prior to initiation of any study-specified procedures. A central reviewer and the sponsor will review eligibility criteria for all subjects.

A standard multi-lead video-EEG with HV and photic stimulation (PS) will be obtained over 30 minutes and will be followed by an additional 6-hour awake video-EEG (total, 6.5 hours). Subjects will undergo HV for 5 minutes (HV period 1). If no absence seizure occurs, the subject will rest for 5 minutes and then undergo HV for an additional 5 minutes (HV period 2). Further details, including procedures for HV and PS will be elaborated in the EEG Charter.

Subjects will begin documenting absence seizure-free days in a daily diary and will continue to do so for the duration of the study. See [Table 3](#) for a detailed list of assessments to be performed.

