### 7.2.2 Visit 1 (Day 0 - Baseline)

Subjects will return to the clinic within 28 days of screening. Following confirmation of continued eligibility by the central reviewer and sponsor, subjects will receive the first dose of study drug (2 mg or placebo) with food and undergo assessments as detailed in Table 3. Subjects will be followed for adverse events, orthostatic vital signs, and ECG for at least 2 hours prior to discharge. The investigator or qualified designee will make the determination of whether it is safe to release the subject from the clinic. Subjects will be instructed to take the second daily dose of study drug no sooner than 10 hours and no later than 14 hours (every 12 hours  $\pm$  2 hours) from the time of their first dose.

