#### **7.2.8      End of Study Visit (Day 26)**

Subjects will return to the clinic for the final visit assessments detailed in [Table 3](#). This visit may take place on Day 25, 26, or 27 as needed for scheduling. Subjects will be instructed to take their dose of study drug before reporting to the clinic.

A standard multi-lead video-EEG with HV and photic stimulation (PS) will be obtained over 30 minutes and will be followed by an additional 6-hour awake video-EEG (total, 6.5 hours). During this time, safety assessments, as shown in Table 3, will be conducted, and 2 PK blood samples, separated by >2 hours, will be obtained. Subjects will undergo HV for 5 minutes (HV period 1). If no absence seizure occurs, after a 5-minute rest, subjects will undergo HV for an additional 5 minutes (HV period 2). Further details, including procedures for HV and PS will be elaborated in the EEG Charter. Adverse events that are unresolved at the visit will continue to be followed by study staff as detailed in [Section 10.2.3](#).

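### No pregnancy test is scheduled on Day 1, so the rule barring pregnant subjects can rest on a Screening result up to 28 days old at first dose

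*Protocol*

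**What the plan says.** Section 10.1.6 of the protocol requires a urine pregnancy test for all women of childbearing potential (WOCBP), confirmed by serum if positive. It sets the entry rule, "Subjects may not enter the study if pregnant", and stops dosing on a positive test during the study. It names no visit.

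The visits come from Table 3. The row "Urine (+/- serum) pregnancy test" is marked at Screening and at Day 26. Its footnote 10 gives only the sequence of tests: "A urine pregnancy test will be performed, and if the result is positive a serum pregnancy test should be completed".

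On the interval before dosing, section 7.2.1 says "The Screening Visit must be performed within 28 days of Visit 1/baseline". On what must happen at Visit 1, section 7.2.2 says "Following confirmation of continued eligibility by the central reviewer and sponsor, subjects will receive the first dose of study drug". Table 3 also marks the eligibility criteria on Day 1. Neither place ties that confirmation to a pregnancy test.

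**The concern.** Pregnancy can begin during a four-week screening period, and a very recent conception can be missed by the Screening test. On Day 1 the plan repeats vital signs, ECG, chemistry, hematology, the C-SSRS and the eligibility review, but not the pregnancy test.

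Inclusion criterion 8 (section 6.2) asks for contraception from the earliest feasible point in screening, not before it, so part of the interval may be unprotected. An unrecognised pregnancy could then be dosed through the whole titration to 10 mg BID. The test that would trigger discontinuation falls when dosing is ending anyway. What is at stake is fetal exposure to study drug in a trial whose own rule is that pregnant subjects do not enter.

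**Working it through.** **1. Is the blank Day 1 cell real?** Marks in three rows of Table 3, read by column:

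| Row | Screening | Day 1 | Day 26 |
|---|---|---|---|
| Clinic visit | X | X | X |
| Pregnancy test | X | – | X |
| Drug screening | X | – | X |

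The drug-screen row has the same pattern as the pregnancy-test row, and section 10.1.5 puts the drug-screen visits in words: "at the Screening Visit and at the Day 26 Visit". The column reading is therefore right, and the blank is not a conversion fault.

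**2. Does anything else supply a Day 1 test?**
- Footnote 10 gives no timing.
- The laboratory panel in 10.1.4 lists no pregnancy test.
- Section 7.2.2 requires eligibility to be confirmed but names no test.
- The telephone checks (7.2.4 to 7.2.7) ask about health status and adverse events only.
- The amendment 3 schedule in SAP section 1.2 marks the test at Screening and once at the end of treatment, with Day 1 blank.

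**3. Age of the last result at first dose.** The protocol's own figure is a 28-day window. The SAP's study-day definition (3.3.7) has no Day 0, so Day -28 is 28 days before Day 1, which agrees. The range is 1 day (screened on Day -1) to 28 days (screened on Day -28).

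**4. Time to the next scheduled test.** From Day 1 to Day 26 is 25 days. Section 7.2.8 adds a window: "This visit may take place on Day 25, 26, or 27 as needed for scheduling". That makes it 24 to 26 days. For a subject screened on Day -28, the two tests are 28 + 25 = 53 days apart (52 to 54 with the window).

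**5. Exposure before that test.** The doses are those of section 4.3, in 2 mg capsules. Footnote 20 sets the end of dosing: "Study drug will be administered on an outpatient basis on the evening of Day 1 through the morning of Day 26".

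- Visit on Day 26, last dose that morning:
  - Capsules: 2×2×1 + 6×2×2 + 6×2×3 + 6×2×4 + 5×2×5 + 5 = 4 + 24 + 36 + 48 + 50 + 5 = 167
  - Amount: 167 × 2 = 334 mg
  - Doses: 25×2 + 1 = 51
- Visit on Day 25, last dose that morning:
  - Capsules: 4 + 24 + 36 + 48 + 4×2×5 + 5 = 157
  - Amount: 157 × 2 = 314 mg
  - Doses: 24×2 + 1 = 49

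**6. What the documents say about hazard (Appendix C).** The evidence is mixed. Rats showed reduced fetal weight at 100 mg/kg/day and above. Rabbits showed no developmental toxicity up to 300 mg/kg/day. Neither embryo-fetal study has toxicokinetics. A separate rat fertility study gives exposure at 100 mg/kg/day of 247 µM·hr total and 2.0 free, against anticipated human exposure at 10 mg BID of 13.6 and 0.054. The margins are 247/13.6 = 18.2 and 2.0/0.054 = 37, as tabulated.

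**7. Effect of a Day 1 predose test.** The age of the last result at first dose becomes 0 days. For a subject screened on Day -28, the 53-day gap splits into 28 days before dosing and 25 days during it.

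**The case against.** The strongest reply is that this is a design choice with several controls around it. A Screening test can be said to serve a rule about entering the study, and nothing in the documents demands a Day 1 test. Contraception is required, eligibility is confirmed again before dosing, pregnancy ends treatment, and an unscheduled test is not barred. Sites also submit an eligibility checklist (section 5.2) that is not among the documents and might ask for a current test. These controls have value, but those that can be read act on a known or reported pregnancy. An unrecognised one needs a test, and none is required. What the checklist contains would be a guess.

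Other parts of the reply stand as limits:
- 28 days is a maximum. Bringing the age of the result to 0 does not bring the risk to 0, because a conception too recent to detect on Day 1 would still be missed.
- Much the same exposure would follow a conception just after Day 1, which the proposed test does not address.
- In the rat embryo-fetal study, transient maternal toxicity was also seen at 300 mg/kg/day and below, and no malformation is listed.
- At most about 15 subjects of both sexes would be treated.
- SAP section 1.1 says no subject enrolled under amendments 4 and 5, so correcting the current text has limited practical reach. The amendment 3 schedule, on which the SAP bases its listings, has the same blank cell.

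The dose count can also be challenged. Section 4.3 gives 10 mg BID through Day 26, and 7.2.8 tells subjects to dose before the visit. With a Day 27 visit that reading gives 4 + 24 + 36 + 48 + 60 + 5 = 177 capsules, 354 mg, 53 doses. Footnote 20 stops dosing on the morning of Day 26, and the SAP says amendment 5 removed Day 27 dosing, so 51 is the better-supported figure.

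**Conclusion.** The concern holds. The only scheduled pregnancy test before dosing is at Screening, up to 28 days before the first dose, and the next is on Day 26. Following the schedule as written could leave an unrecognised pregnancy undetected before dosing and exposed to up to 51 doses (334 mg), or 49 doses (314 mg) if the final visit falls on Day 25. These counts assume full compliance, no dose reduction, and dosing that ends as footnote 20 says.

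The probability is not quantified, since neither the number of WOCBP nor a conception rate is given. The nonclinical evidence shows some fetal effect in one species, at doses whose fetal-study exposure was not measured. No endpoint or analysis changes. It should be fixed because the entry rule depends on a current result and the remedy is cheap.

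**What to change.** Make three edits to the protocol:

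1. In Table 3, mark the existing urine test (footnote 10) at Day 1, predose.
2. In section 10.1.6, state the test visits: Screening, Day 1 predose, and Day 26.
3. In section 7.2.2, require a negative Day 1 result for WOCBP before the first dose.

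The same edits belong in any later protocol built on this text. The cost is one more urine test per WOCBP at an existing clinic visit, and an occasional delay in dosing while a positive result is confirmed by serum. The change adds no test between Day 1 and Day 26, so a conception after Day 1, or too recent to detect then, would still have no scheduled test until the final visit.
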